COVER PAGE

Relation of skin closure method to groin wound infections after proximal femoral artery exposure, a randomized clinical trial

15.3.2018

M.D. [name]
Turku University Hospital
Vascular Surgery Department

Research plan

Relation of skin closure method to groin wound infections after proximal femoral artery exposure, a randomized clinical trial

[name]
TYKS TO3, Verisuonikirurgisen potilaan hoito
[name]
[contact]
[contact]

ABSTRACT

Background: According to published studies the frequency of groin wound infections after peripheral revascularization varies substantially depending on the source from 5% up to 27%.

Aims of the study: The aim of this randomized clinical trial is to evaluate whether the number of groin wound infections can be reduced with an intradermal skin suture compared to the commonly used metal staples skin closure method.

Methods and study design: We will perform a randomized clinical trial of patients undergoing a vascular procedure which includes an incision in the groin. The patients will be randomized (1:1) to two different wound closure techniques: subcuticular suture or metal staples. After the procedure the patients will be controlled for four to six weeks and the infection rate in each group is recorded. A clinical diagnosis of infection according to Centre for Disease Control (CDC) guidelines will be recorded, no microbiological samples will be routinely collected.

Statistical analysis: A power analysis has been conducted based on Finnish RCT studies and a retrospective study from our own hospital (submitted to *Annals of Vascular Surgery* 1/2018) which included all isolated groin wounds from Turku University Hospital Vascular Surgery clinic 2015-2016 and total of 626 patients, 313 per group will be enrolled in the study. Differences in infections between the groups will be evaluated using univariable and multivariable logistic regression analyses.

Time and schedule: This is a multicenter trial. Ethical committee approval was acquired in 2015. The randomization will start in the spring of 2018 in the University Hospital of Turku. Later in the year in the other hospitals that are participating in the study once the regional authorities have given their consent.

Ethical aspects: Ethical committee approval was obtained in 2015. The wound closure techniques are all in everyday use already, nothing new and experimental will be used.

Budget: This study is a critical part of quality control and improvement in vascular surgery. The funding will be applied from the Finnish Academy and EVO funding from the ERVA.

INTRODUCTION

The groin is a common site for arterial access in vascular surgery; it is also a frequently infected wound. According to published articles the frequency of groin wound infections after peripheral revascularization varies substantially depending on the source from 5% up to 27%¹⁻⁵.

Although the percentage of superficial groin infections is considerably high, the incidence of deep infections of the possibly prosthetic graft materials is significantly lower, between 0% and 3.1%⁶⁻⁹

Surgical wound infections (SWI) is defined as an infection that occurs within 30 days of surgery when autogenous material is used, but when prosthetic materials are used the incidence of SWI is calculated for one year after the initial operation. The infection occurs primarily as a result of contamination by skin organisms during or right after surgery. When these pathogens infiltrate deeper into the tissues they can cause an infection of the prosthetic material^{6,10}.

The high incidence of infection after peripheral vascular surgery compared to other clean surgery in both patient- and procedure related. Patients undergoing surgery for peripheral vascular disease are often frail and have typically multiple co-morbidities; they are in high risk for developing post-operative infections. They often have many pre-existing risk-factors for SWI and hospital acquired infections (HAIs)¹¹. This risk is associated with cardiovascular risk factors, degree of ischemia in the operated limb and operative method¹². Procedure related risks include long operation time¹³, which is related to hypothermia, inadequate antibiotic prophylaxis and breaks in sterility. Critical ischemia, rest pain and ischemic ulcer are also independent risk-factors for SWI¹⁴.

SWI causes additional costs for vascular surgery procedures as it lengthens the hospitalization period and requires additional treatments. The length of hospitalization is prolonged by 2-14 days due to SWI^{15,16}. A recent Finnish article concluded that the cost for SWI after a revascularization operation was 3320e².

Numerous studies have been conducted investigating the best infection prevention schemes in vascular surgery. Andrew H. Stewart et al.¹⁷ have done a meta-analysis of 34 studies to determine

the effectiveness of perioperative strategies in infection prevention. They reviewed 34 randomized controlled trials of these 22 were trial of prophylactic systemic antibiotics, 3 of rifampicin-bonded grafts, 3 of preoperative skin antisepsis, 2 of suction wound drainage, 2 of minimally invasive in situ bypass techniques and individual trials of intraoperative glove change and wound closure technique¹⁸. They concluded that systemic prophylactic antibiotics reduced the risk for infection but no significant reduction in other infection prevention methods was discovered

The surgical wound in the groin in vascular surgery is traditionally closed using transdermal closure techniques i.e. metal staples or traditional non-absorbable sutures. Gurusamy et al. ¹⁹ conducted a large Cochrane database review in 2014 on skin closure techniques in all non-obstetric surgery, they concluded that wound dehiscence may be reduced by using subcuticular absorbable sutures. This subcuticular wound closure method is widely adopted to use in for example plastic surgery.

AIMS OF THE STUDY

Patients undergoing peripheral revascularization procedures have many pre-existing risk factors for surgical wound infection. These cannot be reduced. Studies have shown that prophylactic antibiotics can reduce the number of surgical wound and infections and other hospital acquired infections. The above-mentioned Cochrane database review also stated that wound dehiscence can be reduced by using subcuticular wound closure methods.

The aim of this randomized clinical trial is to evaluate whether the numbers of surgical wound infections in patients undergoing peripheral vascular revascularization procedures can be reduced using the above-mentioned subcuticular wound closure method compared to the golden-standard metal staples.

METHODS AND STUDY DESIGN

Setting

This is a randomized multicenter clinical trial. The trial is coordinated from the University Hospital of Turku Vascular Surgery Department. The other participating hospitals are North Karelia Central

Hospital, Satakunta Central Hospital and Jyväskylä Central Hospital. These are all large volume central hospitals that manage demanding vascular surgery patients with a 24h on-call vascular surgery resource.

Corresponding researches in the other participating hospitals are:

MD [name], Turku University Hospital

MD, PhD [name], Satakunta Central Hospital([contact])

MD, PhD [name], North-Karelia Central [contact])

MD, PhD [name], Jyväskylä Central Hospital ([contact])

Patient recruitment

The patients enrolled in this trial are patients that have an isolated groin wound (i.e. the groin wound is not a part of a larger wound in the same limb). Only patients that are undergoing primary procedures are included. Emergency procedures (puncture site hematomas) are also excluded from the trial as are patients operated for surgical site infections and pseudoaneurysm.

Randomization

The patients will be randomized (1:1) to two different wound closure techniques: subcuticular suture or metal staples. The type of subcuticular suture material is not standardized, all participating hospitals use whatever suture they are accustomed to. After the procedure the patients will be controlled for four to six weeks and the infection rate in each group is recorded. A clinical diagnosis of infection according to Centre for Disease Control (CDC) guidelines will be recorded²⁰, no microbiological samples will be routinely collected.

Data recording

The following data will be collected from the operation monitoring system to an Excel-file: age, gender, diagnosis and body mass index (BMI) of the patient, indication and urgency of the operation and whether it was performed by the hybrid or a traditional approach. It will be recorded whether the prophylactic antibiotic was given accordingly. Known risk factors for SWI are recorded from the patient data system, these included peripheral artery disease (PAD), presence of critical limb ischemia (CLI), hypertension, diabetes, rheumatoid arthritis, smoking and

immunosuppressive medication. The condition of the patients' skin will also be recorded in the file.

Statistical analysis

A power analysis has been conducted based on a prospective Finnish study² and a retrospective study from our own hospital (submitted to *Annals of Vascular Surgery* 1/2018) which included all isolated groin wounds from Turku University Hospital Vascular Surgery clinic 2015-2016. Sample size calculations were based on two-sided Pearson's χ^2 -test for two proportions. Sample size was calculated from an estimated infection rate of 20% in the transdermal wound closure group. A decrease of 10 percentage points in infection rate is considered clinically important difference leading to estimated 10% infection rate in the intradermal wound closure group. To detect this difference with a power of 0.9 (1- β) and two-sided significance level (α) of 0.05 266 patients per group is needed. With an estimated drop-out rate of 15% total of 626 patients, 313 per group will be enrolled in the study. Sample size calculations were performed using Power procedure in SAS System for Windows, Version 9.4 (SAS Institute Inc., Cary, NC).

Categorical variables of the study will be characterized by group using frequencies and percents and for continuous variables means and standard deviations or medians with range and 25th and 75th percentiles will be used. Differences in patient characteristics between groups will be tested using two-sample t-test or Pearson's χ^2 -test. Differences in infections between the groups will be evaluated using univariable and multivariable logistic regression analyses. The study site differences will be evaluated in statistical models and if major differences are detected, then study site will be taken into account in the analyses. Two-sided p-values less than 0.05 will be considered statistically significant. The subjects with missing data will automatically be excluded from the analyses of the variables in concern. Statistical analyses will be performed using SAS System for Windows, Version 9.4 or later (SAS Institute Inc., Cary, NC).

TIME AND SCHEDULE

This is a multicenter trial. Ethical committee approval was acquired in 2015. The randomization will start in the spring of 2018 in the University Hospital of Turku. Later in the year in the other hospitals that are participating in the study once the regional authorities have given their consent.

Based on our retrospective material our clinic has ca. 130 patients annually undergoing a procedure with an isolated groin wound. Our estimates are that it will take approximately 2 years between the four participating centers to gather the needed patient material. By this calculation the material should be ready and analyzed during years 2020- 2021.

ETHICAL ASPECTS

Ethical committee approval was obtained already in 2015 for the University Hospital of Turku. The consent from the local ethical authorities has been filed for the other participating hospitals in the beginning of 2018. The wound closure techniques are all in everyday use already, nothing new and experimental will be used.

BUDGET

This study is a critical part of quality control and improvement in vascular surgery. The funding will be applied from the Finnish Academy and EVO funding from the ERVA.

REFERENCES

6. Piano G. Infections in lower extremity vascular grafts. *Surg Clin North Am.* 1995;75(4):799-809.

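### Does leaving the suture material to each hospital, without listing it among the recorded data, undermine the comparison with staples?

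*Protocol*

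**What the plan says.** The Randomization section of the Protocol defines the comparison: "The patients will be randomized (1:1) to two different wound closure techniques: subcuticular suture or metal staples". It then makes the choice of material explicitly local: "The type of subcuticular suture material is not standardized, all participating hospitals use whatever suture they are accustomed to".

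The aim, in Aims of the study, is whether infections "can be reduced using the above-mentioned subcuticular wound closure method compared to the golden-standard metal staples". In the Introduction, the conclusion of the cited systematic review is that "wound dehiscence may be reduced by using subcuticular absorbable sutures". The Aims section restates that conclusion for subcuticular closure in general, naming no material, immediately before it states the aim. The Abstract likewise specifies only an intradermal or subcuticular suture.

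The Data recording list opens with "The following data will be collected from the operation monitoring system to an Excel-file". It covers patient characteristics, indication, urgency, approach, antibiotic prophylaxis, risk factors and skin condition, but not suture type. Hospital is available to the analysis, because under Statistical analysis "The study site differences will be evaluated in statistical models".

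**The concern.** Three things together look like a gap.

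- The rationale cites evidence on absorbable subcuticular sutures, while the methods fix neither absorbability nor any other property of the suture.
- The reference list includes a randomised trial titled "Effect of triclosan-coated sutures on the incidence of surgical wound infection after lower limb revascularization surgery: a randomized controlled trial", so suture coating has been studied for this outcome in related surgery.
- The listed data would not show which suture a patient received.

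If materials differed in infection risk, one pooled rate in the suture group could hide quite different rates by material. A reader could then neither say which suture the result belongs to nor check whether the benefit holds for a given type. At stake would be the interpretation and reproducibility of the result.

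**Working it through.** **1. Is the randomised contrast affected?** The material is used only in patients allocated to suture. It is therefore part of the intervention, not a baseline factor that could differ between the groups by chance or selection. If hospital *h* contributes a share *w_h* of patients and its local suture gives a risk difference *d_h* against staples, the trial estimates the average Σ *w_h d_h*. That is the effect of subcuticular closure with locally used sutures, and it is unbiased whatever the *d_h* are. It is also what the aim asks for.

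**2. Is the sample size affected?** Inputs from Statistical analysis: 20% and 10%, two-sided α 0.05, power 0.90, 15% drop-out.

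n = [1.960·√(2·0.15·0.85) + 1.282·√(0.2·0.8 + 0.1·0.9)]² / 0.10² = (0.990 + 0.641)² / 0.01 ≈ 265.9, so 266 per group.

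266 / 0.85 = 312.9, so 313 per group and 626 in total, as stated. Power at 266 per group is 0.900. Only the two arm rates enter. A mixture of sutures averaging 10% has the same power as a single suture at 10%.

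**3. Would recording the material answer the question about material?** The Protocol gives no rates by suture, so this step uses assumptions.

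- *Share.* The Time and schedule section says that "our clinic has ca. 130 patients annually undergoing a procedure with an isolated groin wound". Over two years that is 2 × 130 = 260, and 260/626 = 41.5% if every eligible patient there enrols. Suppose, for illustration only, that this share is treated in hospitals using coated sutures. Per group that is 0.415 × 266 ≈ 110 coated and 156 uncoated.
- *Rates.* Staples 20% everywhere, suture group averaging 10%, coated-to-uncoated risk ratio RR. The uncoated rate is u = 0.10 / (0.585 + 0.415·RR) and the coated rate is c = RR·u. RR 0.6 gives 12.0% and 7.2%; RR 0.8 gives 10.9% and 8.7%.
- *Test of whether the effect differs between strata.* With staples equal in both strata, the difference in risk differences is u − c, with SE = √[(0.16 + u(1−u))/156 + (0.16 + c(1−c))/110].

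| RR | u − c | SE | ratio | power (two-sided 0.05) |
|---|---|---|---|---|
| 0.6 | 4.8 points | 6.1 points | 0.78 | 12% |
| 0.8 | 2.2 points | 6.2 points | 0.35 | 6% |

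The second figure is barely above the 5% expected with no difference at all. Even with suture type recorded, these two mixtures could not be told apart.

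**4. Would suture against staples within the uncoated stratum help?** With 156 per group, the formula in step 2 gives 70% power for 20% against 10%. But 10% in that stratum presupposes that coating has no effect. With the uncoated rates from step 3, power is 49% (12.0%) or 60% (10.9%).

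**5. Does the aim contradict the methods?** The aim refers back to the method mentioned above. The nearest mention, in the same section, is subcuticular closure without a material qualifier. The absorbable suture appears further back, as the conclusion of a cited review. The Randomization section then states the local choice openly. The three places can be read together without conflict.

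**The case for a change.** The strongest case for a finding is that an analysis plan cannot recover a variable that was never collected, and that two or three fields completed at the end of the operation would cost almost nothing. The comparison of suture with staples within hospitals sharing a customary suture is itself randomised, so it could show whether the benefit holds where a given type is used, without any causal claim about materials. Another hospital would also want to know what was actually used.

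Part of this stands. Naming the sutures would make the report more useful, and a patient-level record would catch surgeons who depart from their hospital's habit. But the list under Data recording covers baseline and risk data and is not a full case report form, so absence from it does not show that the item goes uncollected. The Protocol describes a habit of the hospital, and hospital is known for the analysis. With four centres the customary sutures can be learned by asking, even afterwards. The coating argument has little to rest on: nothing in the Protocol says that any participating hospital uses coated sutures or that coating lowers infection. What remains is a suggestion for description.

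**Conclusion.** The concern does not hold. The Protocol makes an open, pragmatic choice of suture. Its aim asks about the closure technique, and its randomised comparison and sample size answer that question without bias from the material and with the stated 90% power at the assumed 20% and 10%. No stated number, rule or conclusion is wrong. Whether the effect depends on material is a question this trial does not ask. It could not answer it by recording the suture either: material is not randomised, goes with hospital across four sites if each keeps to its own suture, and in the illustration a test for dependence has 6% to 12% power.

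Those power figures rest on an assumed 41.5% coated share, risk ratios of 0.6 to 0.8 and a staple rate of 20% in every hospital. The conclusion itself does not depend on them, since it follows from the aim and the randomisation. The one limit is on wording: the result applies to subcuticular closure with the sutures these hospitals use, and the Protocol's own description already implies this.

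### Does leaving the infection assessor and the recorded CDC criteria unnamed bias the comparison of staples with suture?

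*Protocol*

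**What the plan says.** The outcome procedure stands in the Randomization subsection of Methods and study design. On follow-up: "After the procedure the patients will be controlled for four to six weeks and the infection rate in each group is recorded". On the definition: "A clinical diagnosis of infection according to Centre for Disease Control (CDC) guidelines will be recorded", with a reference to the published CDC definitions. On laboratory confirmation: "no microbiological samples will be routinely collected". The Abstract says the same.

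The arms are subcuticular suture and metal staples, allocated 1:1. The Statistical analysis section treats them as intradermal and transdermal closure: "Sample size was calculated from an estimated infection rate of 20% in the transdermal wound closure group", and the target difference of 10 percentage points is described as "leading to estimated 10% infection rate in the intradermal wound closure group".

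The Data recording subsection lists baseline, operative and risk-factor items, together with antibiotic prophylaxis and skin condition. Infection itself is not on that list. The arms are compared on infection by logistic regression.

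No section names the assessor or mentions blinding, a second reader or adjudication.

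**The concern.** Infection is the only outcome compared between the arms. It is a clinical judgement without routine microbiology, and the treatments leave different marks on the skin. The surgeon who closed the wound knows the arm. Because the outcome sentences are in the passive voice, nothing prevents that surgeon from making the diagnosis, and nothing asks for the CDC criteria that were met. If wounds were judged differently by arm, the comparison could be biased either way. The protocol hopes for fewer infections with suture, yet describes its question as the "subcuticular wound closure method compared to the golden-standard metal staples", so it favours neither direction.

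The timing also makes the point look urgent. Who examines the wound and what is written down are matters of conduct, and a statistical analysis plan cannot recover signs that were never recorded.

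**Working it through.** **The plan's own figure.** Inputs from Statistical analysis: 20% v 10%, two-sided α 0.05, power 0.90, Pearson χ² test, 15% drop-out. With mean rate 0.15:

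n = [1.960·√(2·0.15·0.85) + 1.282·√(0.20·0.80 + 0.10·0.90)]² / 0.10² = (0.990 + 0.641)² / 0.01 ≈ 265.9, so 266 per group.

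Enrolment: 266/0.85 = 312.9, so 313 per group and 626 in total. Both figures reproduce, and power at 266 is 0.900.

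**What unequal judging would do.** Assume that a share c of uninfected wounds in an arm is called infected. The apparent rate is p + (1 − p)·c. The probability of significance in favour of suture is 1 − Φ[(1.960·SE₀ − d)/SE₁], where d is the apparent difference, SE₀ the pooled and SE₁ the unpooled standard error, at 266 per group. The range c = 2 to 5% is an assumption.

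| Scenario | Apparent rates, staples v suture | Probability of significance favouring suture |
|---|---|---|
| No effect (20% both), no over-calling | 0.200 v 0.200 | 0.025 |
| No effect, staples only, c = 2% | 0.216 v 0.200 | 0.066 |
| No effect, staples only, c = 5% | 0.240 v 0.200 | 0.198 |
| No effect, suture at half of c = 2% | 0.216 v 0.208 | 0.041 |
| No effect, suture at half of c = 5% | 0.240 v 0.220 | 0.079 |
| True 20% v 10%, no over-calling | 0.200 v 0.100 | 0.900 |
| True 20% v 10%, suture only, c = 2% | 0.200 v 0.118 | 0.736 |
| True 20% v 10%, suture only, c = 5% | 0.200 v 0.145 | 0.389 |
| True 20% v 10%, staples at half of c = 2% | 0.208 v 0.118 | 0.804 |
| True 20% v 10%, staples at half of c = 5% | 0.220 v 0.145 | 0.611 |
| True 20% v 10%, equal c = 2% | 0.216 v 0.118 | 0.860 |
| True 20% v 10%, equal c = 5% | 0.240 v 0.145 | 0.795 |

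Worked line for c = 5% in staples only: d = 0.040, SE₀ = √(2·0.22·0.78/266) = 0.03592, SE₁ = √((0.1824 + 0.1600)/266) = 0.03588. Then (0.0704 − 0.0400)/0.03588 = 0.847, and 1 − Φ(0.847) = 0.198.

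Numbers of wounds: 266·0.8·c is 4.3 to 10.6 with no effect; 266·0.9·c is 4.8 to 12.0 in a suture arm with a true rate of 10%.

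**What naming a non-operating assessor would recover.** Let r be the share of the differential over-calling that persists when someone else, who can still see the closure, makes the diagnosis. With r = 1 nothing is recovered; with r = 0 everything is. In the one-arm null scenario the gain therefore lies between 0 and 0.066 − 0.025 = 0.041 at c = 2%, and between 0 and 0.198 − 0.025 = 0.173 at c = 5%. The protocol gives no value for c or r, nor for who follows patients up now. If ward or outpatient staff already diagnose, the gain is zero whatever c is.

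**What the text shows about the record.** The Randomization subsection says the diagnosis is recorded, but the Data recording list contains no infection item of any kind. The list therefore cannot be the complete set of captured data, and its lack of fields for CDC criteria does not show that they go unrecorded. Logistic regression fixes a binary analysis variable; it does not limit what is captured.

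**The case for a change.** The strongest reply is that a cited definition says what counts as infection but not who applies it, and leaves no trace of whether it was applied alike in both arms. Separating assessor from operator is the one simple safeguard in a trial where full blinding may be impractical. It would cost two sentences and a short checklist, with no extra patients. The planned check for site differences does not help, since it addresses hospitals and not arms. The table shows that roughly 4 to 12 wounds judged differently could create or hide a result.

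Part of this stands. The assessor is not named, blinding is not mentioned, and the arithmetic is right. A differential error of the assumed size would matter, and the analysis could not remove it.

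The rest does not carry a change. The table measures the harm of an assumed error, not the benefit of the remedy. The larger figures put all the error in one arm; with the other arm over-called at half the rate they fall to 4–8% false benefit and power 0.80–0.61. A colleague who did not operate can still see the closure, and a checklist completed by that same person shows which criteria were ticked, not whether the signs were read alike in both arms. The remedy might also require follow-up to be rearranged at four hospitals, and the document gives no basis for costing that. How much discretion the CDC definition leaves cannot be judged from this document either.

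**Conclusion.** No change to the plan follows. The protocol leaves the assessor and the detail of the infection record unspecified. That is missing detail, not a rule that gives a wrong answer. It names a published definition, and recording the criteria met is what sites would normally do when completing a form for a diagnosis made under that definition. The worrying version, in which the closing surgeon enters an unsupported yes or no, is compatible with the text but not stated in it.

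The size of the possible harm (false benefit of suture in about 7–20% of trials, or power down to 0.74–0.39) rests wholly on an assumed 2–5% over-calling confined to one arm. The part a non-operating but unblinded assessor would recover may be nil and cannot be estimated from the document. The figures of 266 evaluable and 313 enrolled per group stand. Unequal judging by arm remains a limitation of an unblinded clinical outcome, to be kept in mind when the result is interpreted.

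### The automatic exclusion rule drops patients with a known infection outcome from the adjusted comparison of the arms: a small but avoidable loss of precision (minor)

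*Protocol*

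**What the plan says.** All of the relevant text is in the protocol, under Methods and study design.

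- Statistical analysis, missing data: "The subjects with missing data will automatically be excluded from the analyses of the variables in concern". The sentence does not separate a missing infection outcome from a missing covariate.
- Statistical analysis, comparison of the arms: "Differences in infections between the groups will be evaluated using univariable and multivariable logistic regression analyses". Neither model is named as primary, and the covariates of the multivariable model are not listed.
- Statistical analysis, sample size: a two-sided Pearson chi-square test of 20% against 10%, alpha 0.05, power 0.9, 266 per group. Then: "With an estimated drop-out rate of 15% total of 626 patients, 313 per group will be enrolled in the study".
- Data recording lists the candidate covariates. They include "age, gender, diagnosis and body mass index (BMI) of the patient, indication and urgency of the operation", the type of approach, antibiotic prophylaxis and skin condition. For the comorbidities, "Known risk factors for SWI are recorded from the patient data system"; among them are "peripheral artery disease (PAD), presence of critical limb ischemia (CLI), hypertension, diabetes, rheumatoid arthritis, smoking and" immunosuppressive medication.

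**The concern.** In a multivariable model the variables concerned are all those in the model. Applied there, the rule is complete-case deletion: one blank covariate removes the whole record, including an arm and an outcome that are both known. Small gaps in single covariates add up across those that enter the model. The items come from two routine hospital systems at four hospitals, so some gaps are plausible, although the protocol gives no rate.

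Two things are at stake. First, outcome data already collected are lost to one of the two stated comparisons of the arms. Second, the unadjusted and adjusted odds ratios may rest on different patients. If they disagree, part of the disagreement may come from the change of patients. Keeping the same patients removes that part only, because adjusted and unadjusted logistic odds ratios differ even in identical patients.

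**Working it through.** **1. The plan's own figure.** Inputs from Statistical analysis: p1 = 0.20, p2 = 0.10, two-sided alpha 0.05, power 0.90.

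n = [1.960 × √(2 × 0.15 × 0.85) + 1.2816 × √(0.20 × 0.80 + 0.10 × 0.90)]² / 0.10²
= (0.9897 + 0.6408)² / 0.01 = 265.9, so 266 per group.

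Drop-out: 266 / 0.85 = 312.9, so 313 per group and 626 in total. The stated figures reproduce. In reverse, 313 × 0.85 = 266.05: the allowance covers drop-out and leaves nothing for covariate gaps if drop-out does reach 15%.

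**2. Which comparison is affected.** The chi-square test and the univariable model need only arm and outcome. Covariate gaps remove nobody from them, so the power of 0.90 at 266 per group stands. Only the multivariable model loses patients.

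**3. How gaps add up (assumed rates).** If k covariates in the model are each missing independently in a share m of patients, the share deleted is 1 − (1 − m)^k.

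- k = 5, m = 1%: 1 − 0.99⁵ = 4.9%.
- k = 8, m = 1%: 1 − 0.99⁸ = 7.7%.
- To delete 10% with k = 5, m must be 1 − 0.90^(1/5) = 2.1%. To delete 20%, m must be 1 − 0.80^(1/5) = 4.4%.

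Independence is near the worst case: gaps that cluster in the same patients delete fewer.

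**4. Cost to the adjusted comparison (simulation).** Assumptions: 266 per group, 20% against 10%, two normal covariates (log odds ratio 0.3 per SD), three binary covariates at 30% prevalence (log odds ratio 0.4), values missing completely at random, Wald test, 6,000 trials per row.

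| Patients deleted | Power, deletion | SE of log OR, deletion | Power, mean fill-in | SE, mean fill-in |
|---|---|---|---|---|
| 5% | 0.900 | 0.273 | 0.914 | 0.266 |
| 10% | 0.880 | 0.281 | 0.913 | 0.266 |
| 20% | 0.837 | 0.299 | 0.910 | 0.266 |

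With no treatment effect (15% in both arms) and 10% or 20% affected, the type I error is 0.050 or 0.052 with fill-in and 0.047 or 0.051 with deletion. A repeat run under the same assumptions gave power 0.895, 0.877 and 0.843 with deletion. It gave 0.90 to 0.92 with mean fill-in or with a missing category for categorical covariates.

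**5. Check by hand.** The standard error should grow as 1/√(share kept): 0.266/√0.95 = 0.273, 0.266/√0.90 = 0.280, 0.266/√0.80 = 0.297. Power of 0.913 with everyone kept corresponds to an effect of 1.960 + 1.360 = 3.320 standard errors. Multiplying by √0.95, √0.90 and √0.80 gives 3.236, 3.150 and 2.969. Subtracting 1.960 gives normal probabilities of 0.90, 0.88 and 0.84, in agreement with the simulation.

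**The case against.** The strongest reply is that little is at risk. The powered comparison is unadjusted and loses nobody. At about 5% deletion the adjusted test still has power of about 0.90. A visible loss needs some 10% to 20% of patients to lack a model covariate, and nothing in the protocol suggests that. If drop-out is below plan there is slack: with 5% drop-out and 10% lacking a covariate, 313 × 0.95 × 0.90 = 267.6 per group remain in the adjusted model. All of this stands, and it is why the point is minor.

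A second reply concerns the remedy. A separate missing category can be too sparse to help. At 1% missing it holds about 5 of 532 patients, and at an overall infection rate of 15% it contains no infection with probability 0.85⁵ = 0.44. Those patients then add nothing to the treatment odds ratio, as if they had been deleted. This stands in principle and shapes the fix below, although missing categories cost almost no power in the simulation.

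A third reply is that a statistical analysis plan may deal with this. The protocol does not leave the matter open, however. It states a rule, and a plan that did otherwise would contradict it.

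Four stronger readings are tempting but unsupported:

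- *The trial's stated power falls below 0.9.* It does not. The sample size rests on the unadjusted test, which covariate gaps do not touch.
- *Everything under Data recording enters one model, so deletion is large.* The protocol lists these items as recorded and does not say which enter the model.
- *Deletion is what makes the adjusted log odds ratio less precise than the unadjusted one.* Logistic adjustment alone raises its standard error from 0.258 to 0.266 with nothing missing. Deletion only widens that gap.
- *Excluding patients without an outcome biases the result.* The documents do not show that loss to follow-up would depend on infection and arm.

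**Conclusion.** The concern holds in a limited form. As written, the rule removes patients with a known arm and outcome from the multivariable comparison for one missing covariate in that model, and this can be avoided. No bias is claimed, and the unadjusted comparison is intact.

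Under the stated assumptions adjusted power drops from about 0.91 to 0.90, 0.88 or 0.84 when 5%, 10% or 20% of patients are deleted. The first step merely uses up the small gain in power that adjustment brings over the unadjusted 0.90; the other two go below it. These figures rest on assumed missing rates, an assumed set of five covariates, values missing completely at random, and drop-out at the full 15%. The protocol fixes only the last of these. Severity is minor: a cheap improvement in wording, not an error that endangers the trial's result.

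**What to change.** In the protocol's Statistical analysis section, replace the missing-data sentence, as far as it governs the comparison of the arms, with wording such as:

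*A patient with a known infection outcome stays in the adjusted comparison of the arms. A missing baseline covariate is filled in without use of arm or outcome: a continuous covariate by its mean over both arms together; a categorical covariate by its overall proportion, or by a separate missing category only where that category is large enough to contain infections.*

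The covariates' own odds ratios may still be reported on complete cases and labelled as such, because fill-in serves the treatment comparison and not those estimates.

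Cost: one sentence and a little programming in the SAS version already named, with no extra patients or data. The downside is a simple fill-in assumption for the covariates.
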